#### Prior/Concomitant Medication

Protocol No: ACI-35-1802

Statistical Analysis Plan

Version Date: 05-Dec-2023

SubjectDate of First InjectionStart DateStop DatePrior/Concomitant10010116-Oct-2019xx-Sep-2019xx-xxx-2019Concomitant

NB. Year of stop date is the same as the year of the first injection so medication is assumed to be concomitant.

#### Example 3

		Prior/Concomitar	nt Medication	
Subject	Date of First Injection	Start Date	Stop Date	Prior/Concomitant
100101	16-Oct-2019	14-Sep-2019	XX-XXX-XXXX	Concomitant
NB. Stop Date	NB. Stop Date missing and medication not checked as ongoing, so medication is assumed to be concomitant.			

#### Example 4

		Prior/Concomitar	nt Medication	
Subject	Date of First Injection	Start Date	Stop Date	Prior/Concomitant
100101	16-Oct-2019	xx-Oct-2019	15-Oct-2019	Prior
NB. Although start date partial, stop date is prior to the date of the first injection, so medication is assumed to be prior.				

## 8.12 Handling of Unscheduled Visits Data and Unscheduled Assessments

If scheduled and unscheduled assessments are available for the same parameter within a single visit, then only the last scheduled assessment will be used in the analysis. In case only unscheduled visit and no planned visit is conducted for particular parameters, the unscheduled visit may be mapped to a scheduled visit, only if it is within the visit window as defined in the protocol, and then summarized. This applies, for example, to visits performed by telephone rather than onsite due to Covid-19 lockdown / travel restriction. Scheduled (planned) and unscheduled visits data will be included in listings and the one used in the analysis will be flagged.

The visit window allowed for each particular parameter is specified in the Schedule of Assessments included in the protocol.

In the ECG external data transfer set, ECG repetitions are referenced as unscheduled visits. In such cases, the following rules will be applied:

- The last ECG measurement will be taken for analysis presented in summary tables.
- The listing will show all ECG repetitions at the respective assigned visit.

In case the ECG was done at a scheduled visit where an ECG was not planned, the following rules will be applied in the analysis:

- The ECG results will not be taken into consideration for summary tables.
- The corresponding listing will show these evaluations and flag them with a respective footnote.

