3.3.3 Removal of Subjects from Therapy or Assessment

A subject will be considered to have completed the study when he or she completes the Visit 11 at Week 74 (or the Visit 13 at Week 98 in case of optional post-injection period extension). If a subject is discontinued at any time after randomization into the study, the investigator will make every effort to follow the subject and complete the premature discontinuation assessments as shown in Section 3.5.3.

Additional participants may be recruited to replace withdrawn subjects unless the subject withdrew for safety reasons.

A termination electronic case report form (eCRF) page should be completed for every subject who received investigational product, whether or not the subject completes the study. The reason for any early discontinuation should be indicated on this form.

The primary reason for a subject discontinuing early should be selected from the following standard categories of early termination:

- Adverse Event (Adverse Reaction): Clinical or laboratory events occurred that, in the medical judgement of the investigator for the best interest of the subject, are grounds for discontinuation. This includes serious and non-serious adverse events (AEs) regardless of relation to the investigational product.
- Death: The subject died.
- Withdrawal of Consent:

🕜 AC Immune

- The subject or caregiver desired to withdraw from further participation in the study in the absence of an investigator-determined medical need to withdraw. If the subject gave a reason for withdrawing, it should be recorded in the eCRF. In case of caregiver withdrawal, the subject can continue in the study if a new caregiver consents to act in this role.
- In the Netherlands, subjects who become unable to maintain their decisional capacity during the course of the study as assessed with the MacCAT-CR interview (refer to section 3.5.6 and 6.1.3).
- Protocol Violation: The subject's findings or conduct failed to meet the protocol entry criteria or failed to adhere to the protocol requirements (e.g., drug noncompliance, use of prohibited concomitant treatment (section 3.4.7.2), failure to return for a defined number of visits). The violation is important enough to justify early discontinuation since it would hamper the evaluation of the primary endpoints of the study.
- Lost to Follow-up: The subject stopped coming for subsequent study visits and study personnel were unable to contact the subject.

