3.5.2.23 Unscheduled Visit (UV)

At any time during the study, subjects might be invited to the site for additional visits (e.g. further evaluation needed following a phone call with the subject). In case of safety concerns, as per investigator assessment during a scheduled "Phone call" or a visit of the post-injection period extension (if applicable) with the subject, an additional visit will be scheduled in order to further assess the event(s). Any subjects attending an unscheduled visit should at a minimum complete the following safety related assessments:

- Provide information on new AEs/SAEs since last visit.
- Provide information on new concomitant medication since last visit.
- Be examined for the Vital signs
- Go through physical and neurological examination
- Have blood withdrawn for standard safety evaluation

Upon investigator's medical judgement, other assessments considered as needed can be performed during those visits (MRI, ECG, etc.).

Due to the resurgence of the pandemic in multiple participating countries since September 2020 and in case the subject and caregiver cannot travel to the site due to Covid-19 restriction, the Unscheduled Visit and related assessments will be performed at subject's home if feasible and locally permitted (see details under 3.5.1.1 Alternative Mode of Administration of Assessments to Reduce Safety Risks due to Participation during Covid-19 pandemic).

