3.5.3 Assessments for Premature Termination

Any subject, who withdraws from the study prior to completion (see standard categories of early termination under section 3.3.3), will be encouraged to at least complete the safety assessment evaluation (see detail under 3.5.2.21 Unscheduled Visit) by attending a last visit.

If this is not possible, subject will be asked to at a minimum, provide the reason for withdrawal and provide information on any adverse events that might have arisen since the last visit and the outcome of any previously recorded AEs.

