#### 11.5.2 Laboratory Data

The following safety laboratory data will be collected for this study:

- Routine hematology [red blood cell count, hemoglobin, hematocrit, red cell indices, white blood cell count (including differential), platelet count], coagulation [prothrombin time (PT), international normalized ratio (INR), activated partial thromboplastin time (APTT)] and biochemistry evaluations [Sodium, potassium, chloride, urea, creatinine, calcium, inorganic phosphate, glucose, total bilirubin, total protein, albumin, aspartate aminotransferase, alanine aminotransferase, alkaline phosphatase, Gamma-glutamyl Transferase (Gamma GT), creatine kinase, cholesterol, triglycerides and uric acid and C-Reactive Protein (CRP)] in blood
- Routine biochemistry evaluations in urine [pH, protein, glucose, ketones and blood]
- Inflammatory markers in blood [CRP] and Cerebrospinal Fluid (CSF) [protein, CSF/serum albumin ratio, IgG + IgM Index, Oligoclonal bands, glucose, cell count and differential count]
- Autoimmune antibodies in blood [Anti-nuclear Antibodies (ANA), Anti-double stranded DNA Antibodies (Anti-dsDNA)]
- Serology (HIV-1/2 Antibody, Hepatitis B Virus Surface Antigen, Hepatitis C Virus Antibody, Rapid Plasma Reagin (syphilis))

Statistical Analysis Plan Version Date: 05-Dec-2023

 Other laboratory tests (U1-nRNP Ab, Anti-Ro (SS-A Ab), Anti-La (SS-B Ab), Complement C1q Antibody, C3c, Complement C4)

The actual values and change from baseline, see Sections 8.2 and Section 8.3 for definitions, for all continuous laboratory parameters above will be summarized per treatment group, by visit [Baseline, Visit 2 (Week 2), Visit 3 (Week 8), Visit 4 (Week 10), Visit 5 (Week 24), Visit 6 (Week 26), Visit 7 (Week 36), Visit 8 (Week 48), Visit 9 (Week 50), Follow-up Visit 10 (Week 67) and Follow-up Visit 11 (Week 74)] [TFL Shell Table 14.3.3.1.1, 14.3.3.2.1, 14.3.3.3.1.1]. Urinalysis categorical data will be summarized separately [TFL Shell Table 14.3.3.1.2]. Serology data, Vitamin B12, folate and thyroid function tests are collected at screening only [TFL Shell Table 14.3.3.4].

Shift tables will present shift from baseline to each subsequent post-baseline visit, i.e. Baseline, as defined in section 8.2 [TFL Shell Table 14.3.3.1.2, 14.3.3.2.2, 14.3.3.3.2].

A box plot will present Hematology and Biochemistry laboratory values per Visit and Treatment Group [TFL Shell Figure 14.4.1, 14.4.2].

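### Exit and recall measurements outside a visit window, or at a visit that already has a scheduled value, are left out of the safety shift tables, and no overall post-baseline row brings them back

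*SAP*

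**What the plan says.** Protocol 3.5.3 says that a subject who withdraws early "will be encouraged to at least complete the safety assessment evaluation (see detail under 3.5.2.21 Unscheduled Visit) by attending a last visit". The section it names, 3.5.2.21, is Visit 12. The Unscheduled Visit is 3.5.2.23, which states: "Any subjects attending an unscheduled visit should at a minimum complete the following safety related assessments". Its list is adverse events, concomitant medication, vital signs, physical and neurological examination, and blood for safety. The same section covers visits arranged after a worrying phone call, and protocol 3.1.5 requires a return to clinic for related events above mild severity.

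SAP 8.12 has two rules for these data. If the same visit also holds a scheduled assessment of the parameter, "then only the last scheduled assessment will be used in the analysis". If there is only an unscheduled one, "the unscheduled visit may be mapped to a scheduled visit, only if it is within the visit window as defined in the protocol". On listings it adds: "Scheduled (planned) and unscheduled visits data will be included in listings and the one used in the analysis will be flagged".

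For laboratory data, SAP 11.5.2 says: "Shift tables will present shift from baseline to each subsequent post-baseline visit". The visits it lists for laboratory summaries run from Baseline through Visits 2 to 11. The shift tables for vital signs (11.5.3), physical examination (11.5.5) and neurological examination (11.5.6) have the same by-visit form. Neither these sections nor the output list in SAP Appendix 2 names an early-termination visit, a last post-baseline value or a worst post-baseline value.

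**The concern.** Unscheduled safety visits are not a random sample of visit days. Many happen because a subject reported a reaction or is leaving the study, and protocol 3.3.3 lists adverse events among the reasons for leaving. A rule that summarises such values only when the date happens to suit a window tends to drop measurements taken because something may be wrong.

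Change from baseline in laboratory values, vital signs and both examinations is among the primary safety endpoints, beside adverse events (protocol 5.3.5, SAP 11.5). For a subject who leaves or is recalled, the shift tables can end with the last value obtained on schedule. The SAP is more inclusive elsewhere: an unscheduled pre-dose value can serve as baseline (8.2, Example 3), and for repeated ECGs the last measurement is analysed (8.12).

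**Working it through.** The plan gives no figure for this point, so there is none to reproduce. The check traces the rules and then counts days.

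**1. Route of an exit or recall value.** Protocol 3.5.3 or a safety phone call leads to the assessments in 3.5.2.23. SAP 8.12 then asks two questions: is the date inside a protocol window, and does that visit lack a scheduled value for the parameter? Only two yes answers allow the value into a summary table, and even then the wording is permissive. Otherwise it is listed only. No other row takes it up.

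**2. Days inside a safety-visit window.** Nominal days and windows come from the Schedule of Assessments, with the first injection as day 0. Visits 4.1, 4.2, 6.1 and 7.1 are omitted because they include no safety laboratory tests, vital signs or examinations.

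| Visit | Nominal day ± window | Days covered up to day 518 |
|---|---|---|
| V2 | 14 ± 3 | 7 |
| V3 | 56 ± 3 | 7 |
| V4 | 70 ± 3 | 7 |
| V5 | 168 ± 7 | 15 |
| V6 | 182 ± 2 | 5 |
| V7 | 252 ± 3 | 7 |
| V8 | 336 ± 7 | 15 |
| V9 | 350 ± 2 | 5 |
| V10 | 469 ± 7 | 15 |
| V11 | 518 ± 7 | 8 (511 to 518) |

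The sum is 91, and 91/518 = 17.6%. The schedule's footnote allows post-injection visits exceptionally up to 28 days after immunization. Counting days 11 to 28 after each injection adds 11 + 11 + 13 + 13 = 48 days, so (91 + 48)/518 = 139/518 = 26.8%. Running the count to day 525, the end of the V11 window, gives 98/525 = 18.7% and 146/525 = 27.8%.

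**3. Effect of the scheduled value taking precedence.** If every visit is done on its nominal day, only the days before that date are in the window of a visit still to come: 3 + 3 + 3 + 7 + 2 + 3 + 7 + 2 + 7 + 7 = 44 days, or 44/525 = 8.4%.

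**4. The days after an injection.** With injections on their nominal days, the next window opens on day 11 (V2 after V1, V4 after V3) or day 12 (V6 after V5, V9 after V8). The V3 window runs to day 3 after its injection, and the V5 and V8 windows to day 7, but those visits already have their scheduled pre-dose values. A visit on days 1 to 10 therefore maps to no open visit. That period includes any recall soon after the 48 to 72 hour call. An injection given late in its window would shorten this gap if windows are counted from the first dose.

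**5. Weight of one subject.** An unexpanded sub-cohort has 6 active subjects, so one subject is 1/6 = 16.7% of an overall post-baseline row.

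**The case against.** The strongest reply is that little of importance is lost. Adverse events head the list of primary safety endpoints and never pass through SAP 8.12. Protocol 4.1.4 requires abnormal findings judged clinically significant to be recorded as adverse events. SAP 11.5.1 then reports numbers and percentages of subjects, including discontinuations of treatment and of the study. A subject who leaves with a significant abnormality is counted there. The listings hold every value, and the DSMB receives listings of abnormal laboratory results, vital signs and new examination abnormalities (SAP Appendix 2). In groups of six, listings can be read subject by subject. All this stands, and it limits the point to the measurement tables.

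The affected group may also be small. Subjects who only stop injections stay in follow-up (protocol 3.1.1) and so can still supply scheduled values. Only full withdrawal triggers 3.5.3, and attendance is merely encouraged. The coding of that last visit as unscheduled is an inference: protocol 3.5.3 borrows the Unscheduled Visit content without giving the visit a label, and the table shells are a separate document. This stands too, although the SAP provides no other category.

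A reader might infer that 73% to 82% of exit assessments (the complements of 26.8% and 17.6%) will be dropped. That would require exit dates spread evenly over follow-up, which nothing in the documents supports. A reader might also say that a by-visit row showing 0/5 should show 1/6. It should not, because a subject who has left has no value at that later visit.

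The reply does not answer one thing. The adverse event route depends on the investigator's judgement of significance, whereas a shift table shows movement out of range without it.

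**Conclusion.** The point holds for the by-visit laboratory, vital-sign, physical and neurological tables. Exit and safety-triggered values enter them only inside a protocol window with no scheduled value for that visit, and there is no overall row to recover the rest. What is missing is the measurement shifts, mainly range shifts not judged clinically significant, for subjects who leave or are recalled for a reaction.

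The documents do not support the stronger reading that the primary safety analysis or the adverse event rates exclude these subjects.

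On size, nominal windows cover about 18% of days to Week 74, or about 27% with the 28-day allowance. Under nominal timing no visit on days 1 to 10 after an injection can be mapped to an open visit. Many such visits would therefore be unmapped, but the documents give no count, so the effect on any table cannot be stated. The conclusion assumes that the exit visit is coded as unscheduled. The change is worth making because it is cheap and the omission is not random.

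**What to change.** - In SAP 8.12, say how the early-termination visit is labelled, and state that early-termination and unscheduled post-baseline values count towards overall post-baseline summaries.
- Add two rows to the hematology, biochemistry, vital-sign, physical and neurological shift tables: *last post-baseline (including early termination)* and *worst post-baseline, scheduled or unscheduled*. For parameters that can be abnormal in both directions, give the lowest and the highest value.
- Add the same rows for urinalysis only where urine was taken, because urine is not in the Unscheduled Visit minimum.
- Use all treated subjects with any post-baseline value as the denominator.
- Leave the by-visit rows as they are, and footnote that subjects with more visits have more chances of an abnormal value.
- Correct the cross-reference in protocol 3.5.3 from 3.5.2.21 to 3.5.2.23.

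The cost is SAP wording, a rule of direction for each parameter, extra rows in existing tables and one corrected reference. No new data are needed and no sample size changes. The worst-value rows will look somewhat less favourable than the by-visit rows.

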#### 11.5.4 Electrocardiogram (ECG)

12-lead ECG recording machines will be provided by the central reading company **Exercise**. Printouts of each ECG must be kept at the site for archiving. **We will manage ECG data** through their Web-based platform. The system allows the acquisition, storage and display of ECG

recordings from the ECG machines so that cardiologists can review them. Please refer to the ECG manual for further details.

Normal, abnormal not clinically significant and abnormal clinically significant results as interpreted by the site will be summarized by Visit (Baseline, as defined in Section 8.2) and Treatment Group (and Overall) [TFL Shell Table 14.3.5.1].

ECG parameters [PR interval (msec), RR interval (msec), QRS duration (msec), QT Interval (msec), QTcB Interval (msec) and QTcF interval (msec)] actual values and change from baseline where baseline and change from baseline are as defined in Section 8.2 and Section 8.3, will be summarized by Visit, and Treatment Group (and overall) [TFL Shell Table 14.3.5.2].

The number and percentage of subjects with an absolute QTcB Interval (msec) ≤480 or >480; and an absolute QTcF interval (msec) ≤480 or >480 will be summarized by Visit, and Treatment Group (and overall) [TFL Shell Table 14.3.5.3].

The number and percentage of subjects with a change from baseline in QTcB Interval (msec) and QTcF interval (msec) <30 or  $\geq$ 30 or  $\geq$ 60 will be summarized by Visit, and Treatment Group (and overall) [TFL Shell Table 14.3.5.4].

Shift table categorizing results as normal, abnormal (clinically significant / not clinically significant) will present shift from baseline to each subsequent post-baseline visit, i.e. Baseline, as defined in Section 8.2 [TFL Shell Table 14.3.5.5].

All ECG data will be listed for the Intention-to Treat Population [TFL Shell Listing 16.2.10.1 and 16.2.10.2].

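### The QTc outlier tables use the last repeat tracing and planned ECG visits only, so they can miss prolonged values; add a worst post-baseline row

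*SAP*

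**What the plan says.** SAP 8.12 sets two ECG-specific rules.

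- **Repeats.** "In the ECG external data transfer set, ECG repetitions are referenced as unscheduled visits". For these, "The last ECG measurement will be taken for analysis presented in summary tables", and "The listing will show all ECG repetitions at the respective assigned visit".
- **Off-schedule ECGs.** "In case the ECG was done at a scheduled visit where an ECG was not planned", the rule is: "The ECG results will not be taken into consideration for summary tables". These tracings are still listed: "The corresponding listing will show these evaluations and flag them with a respective footnote".

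The same section has two general rules. If scheduled and unscheduled assessments exist within one visit, the last scheduled one is analysed. If only an unscheduled visit took place, "the unscheduled visit may be mapped to a scheduled visit, only if it is within the visit window as defined in the protocol".

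SAP 11.5.4 defines the two outlier tables. Table 14.3.5.3 counts subjects with QTcB and QTcF at or below 480 ms against above 480 ms. Table 14.3.5.4 counts changes from baseline below 30, at least 30 and at least 60 ms. Both are by visit and treatment group. Neither SAP 11.5.4 nor the output list in SAP Appendix 2 contains a row or table for the worst, or any, post-baseline value.

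Under SAP 8.2 the ECG baseline is the latest available value before the first injection. Protocol 3.5.2 plans ECGs at Screening, Visit 6 (Week 26), Visit 9 (Week 50) and Visit 11 (Week 74).

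**The concern.** ECG is among the primary safety endpoints (Protocol 2.2.1, SAP 7.1). A categorical QTc table is there to show extremes. A rule that picks one tracing per visit before counting can remove an extreme, and here no other table puts it back.

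The schedule leaves few rows in which an extreme could appear. The first planned post-baseline ECG is at Week 26, after the injections at Weeks 0, 8 and 24. An ECG done at another scheduled visit enters no summary table. In sub-cohort 1.1, Visit 6 became a remote visit for 7 of 8 subjects and assessments needing travel were cancelled (SAP 12.0), so those subjects have no planned ECG between Screening and Week 50.

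Groups are small. With 6 active subjects in an initial sub-cohort, replacing one value moves a cell from 1/6 (16.7%) to 0/6.

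There is also an ambiguity in SAP 8.12. Its general rule prefers the last scheduled assessment, while the ECG rule takes the last repeat, which is coded as unscheduled. The ECG rule reads as an exception but does not say so.

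**Working it through.** The documents give no QTc rate, repeat rate or repeat trigger, so there is no stated figure to reproduce. The check has an exact part and an illustration.

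**1. Exact part, absolute QTc.** At any visit the event {last tracing > 480} is contained in {any tracing > 480}. Hence count(last) ≤ count(any). The inequality is strict whenever some subject has an earlier tracing above 480 and a last tracing at or below it. No assumption is needed.

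**2. Size if values trigger repeats (assumed inputs).** Let a subject's underlying QTc be m ~ N(μ, σ_b²). The first tracing is a = m + e₁ and the repeat is r = m + e₂, with e ~ N(0, σ_w²). One repeat is taken if a > 480. Write p(m) = 1 − Φ((480 − m)/σ_w). Then:

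- any tracing above 480: P(a > 480) = E[p(m)] = 1 − Φ((480 − μ)/√(σ_b² + σ_w²))
- last tracing above 480: P(a > 480 and r > 480) = E[p(m)²]

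Example with μ = 420, σ_b = 20, σ_w = 10: √(400 + 100) = 22.36, 60/22.36 = 2.68, upper tail about 0.37%. Simulation with 2,000,000 draws gave:

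| μ, σ_b, σ_w (ms) | Last > 480 | Any > 480 | Last/any | Underlying m > 480 |
|---|---|---|---|---|
| 420, 20, 10 | 0.12% | 0.37% | 0.32 | 0.14% |
| 430, 20, 10 | 0.50% | 1.28% | 0.39 | 0.62% |
| 430, 25, 15 | 1.79% | 4.34% | 0.41 | 2.29% |
| 440, 20, 10 | 1.72% | 3.69% | 0.47 | 2.27% |

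**3. Size if repeats do not depend on the value.** With a repeat for everyone, the last tracing gives the same rate as a single tracing: 0.37% against 0.37% in the first population and 4.33% against 4.34% in the third. The maximum of the two gives 0.62% and 6.89%.

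**4. Change of at least 30 ms.** Third population, with repeats triggered by a value above 450 ms:

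| Which values are replaced by the last tracing | Change ≥ 30 ms |
|---|---|
| None (single tracings) | 7.87% |
| Baseline only | 9.24% |
| Post-baseline only | 5.88% |
| Both | 6.75% |

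Replacing a high baseline by a later, lower one raises the apparent change; doing the same after baseline lowers it. In all four populations, and with triggers of 450 and 480, the net effect was downward when both ends were replaced and upward when only baseline was.

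**The case against.** Four points on the other side carry weight.

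- **No trigger is documented.** If repeats are taken for lead or recording quality, the last tracing is the sensible one and step 3 shows no bias relative to a single tracing. This stands. It limits the finding to what the table can miss.
- **Part of what is removed is noise.** In step 2 the last-tracing rate is closer than the any-tracing rate to the share of subjects whose underlying QTc exceeds 480. This stands too. A worst-value row shows extremes; it does not estimate how many subjects are truly prolonged.
- **Extremes stay visible elsewhere.** All repeats and off-schedule tracings are listed, clinically significant abnormal assessments are recorded as adverse events (Protocol 4.1.4), and the DSMB receives a listing of abnormal ECGs (SAP Appendix 2). With sub-cohorts of 8 to 25 subjects, listings can be read. This limits the harm but leaves the tables as they are.
- **By-visit tables have no row for an off-schedule ECG.** That is a consequence of the layout, and the rule is pre-specified and the same in every arm. It explains the exclusion, but it is also the reason to add a row that does not depend on visit.

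A reader might infer that every ECG outside the plan is dropped. The text does not say that. The exclusion concerns scheduled visits with no planned ECG, it applies to summary tables only, and an unscheduled visit inside the window may be mapped when the planned one did not take place.

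**Conclusion.** The point holds as a limit on what the tables can show. The above-480 count is at most the all-tracings count, and lower whenever an earlier prolonged tracing was followed by a last tracing at or below 480. If values above 480 trigger the repeat, the table shows 32% to 47% of the worst-value count. That rests on an assumed mean of 420 to 440 ms, between-subject SD of 20 to 25 and within-subject SD of 10 to 15. If repeats are technical, there is no bias relative to a single tracing. For the change table the direction is not fixed.

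Two stronger readings go too far.

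- **That the tables do under-report, and many times over.** For a single subject with a true mean of 470 ms and within-subject SD of 10, p = 1 − Φ(1) = 15.9% and p² = 2.5%, about 6-fold; SDs of 15 down to 8 give about 4- to 9.5-fold. This describes one subject just below the cut-off whose every exceedance is repeated. It does not describe a table, and the documents support neither the mean nor the trigger.
- **That the change table is biased downward.** Step 4 shows that a repeated baseline can push it upward.

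This is a low-cost improvement to a primary safety display.

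**What to change.** 1. Keep the by-visit rows, and keep one value per visit for the table of means and changes.
2. Add a *worst post-baseline* row to Tables 14.3.5.3 and 14.3.5.4: the maximum QTcB and the maximum QTcF over all technically valid post-baseline tracings, including repeats and off-schedule ECGs.
3. State one rule for repeated baseline tracings, for example the mean of the valid pre-dose repeats, and use it in both the by-visit and the worst-value rows.
4. Say in SAP 8.12 that the ECG rule overrides the general rule on scheduled and unscheduled assessments, and give the reason for repeats if it is recorded.

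The tracings are already collected and listed, so the cost is SAP wording and minor programming. Outlier counts will be somewhat higher, and not only because real extremes appear. A maximum rises with the number of tracings (0.37% to 0.62% when everyone in the first population has two), and against a single baseline it also raises the counts of change of at least 30 and 60 ms. A footnote should say so.
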